8. OUTPUT PRESENTATIONS

Appendix 1 shows conventions for presentation of data in outputs.

The shells document provided with this SAP describes the presentations for this study and therefore the format and content of the summary tables, figures, and listings to be provided by IQVIA Biostatistics.

9. DISPOSITION AND WITHDRAWALS

All patients who provide informed consent will be accounted for in this study. Patient disposition and withdrawals, and protocol deviations, including inclusion and exclusion criteria will be presented for RND set. Reasons for exclusion from each analysis set will be presented for the ENR set with patients classified according to randomized treatment.

Protocol deviations will be defined in a separate document. The list will be finalized before database lock.

10. DEMOGRAPHIC AND OTHER BASELINE CHARACTERISTICS

Demographic data and other baseline characteristics will be listed for the ENR set, with patients classified according to randomized treatment, and summarized for the RND set.

No statistical testing will be carried out for demographic or other baseline characteristics.

Document: ...\\Verona_Pharma\\RPL554\\BZA48916\\Biostatistics\\Documentation\\SAP\\Verona CO-205 SAP v1.0

Author: [REDACTED] Version Number: V1.0

Version Date: 05DEC2019

Template No.: CS_TP_BS016 Revision 5

Reference: CS_WI_BS005

Effective Date: 01Apr2018

The following demographic and other baseline characteristics will be reported for this study:

- Age (years) - calculated relative to date of consent
- Age category (<65 years and \geq 65 years)
- Gender
- Ethnicity
- Race
- Height (cm)
- Weight (kg)
- Body mass index (BMI) (kg/m²)
- Reversibility status (reversible or non-reversible) – planned and actual
- Modified Medical Research Council (mMRC) questionnaire scores
- Pre- and post-bronchodilator FEV₁ (both in litres and in percentage of predicted normal)
- Post-bronchodilator FEV₁/FVC
- FEV₁ actual reversibility (in mL and as a percentage)
- Time since initial diagnosis of COPD (years)
- Chronic Bronchitis (yes/no)
- Smoking status (current smoker (yes/no), number of packs per day, number of years smoking, and smoking exposure in pack-years)

10.1. Derivations

- BMI (kg/ m²) = weight (kg)/ height (m)²
- Time since initial diagnosis of COPD = (date of consent - date first diagnosed)/ 365.25
- Smoking exposure (pack-years) = number of packs per day * number of years smoking

Reversibility status is calculated based on pre-dose and post-dose FEV₁ values taken at Screening. If patient has increase of \geq 12% and \geq 200mL then patient is reversible, else patient is non-reversible.

Actual reversibility strata will be decided on the value calculated pre-rounding, however rounded reversibility values will be presented in the outputs. See Appendix 3 for the rounding rules that are used by the Vendor.

10.2. mMRC

Modified Medical Research Council (mMRC) questionnaire is used to assess a patient's level of breathlessness and the score will be listed. The scores range from 0 to 4, with the following definitions:

0 = "I only get breathless with strenuous exercise",

1 = "I get short of breath when hurrying on the level or walking up a slight hill",

Document: ...\\Verona_Pharma\\RPL554\\BZA48916\\Biostatistics\\Documentation\\SAP\\Verona CO-205 SAP v1.0

Author: [REDACTED] Version Number: V1.0

Version Date: 05DEC2019

Template No.: CS_TP_BS016 Revision 5

Reference: CS_WI_BS005

Effective Date: 01Apr2018

2 = “I walk slower than people of the same age on the level because of breathlessness, or I have to stop for breath when walking on my own pace on the level”,

3 = “I stop for breath after walking about 100 meters or after a few minutes on the level”,

4 = “I am too breathless to leave the house, or I am breathless when dressing or undressing”.

11. SURGICAL AND MEDICAL HISTORY

Surgical and Medical History information will be listed and summarized for the ENR set.

- Surgical History will be coded using the Medical Dictionary for Regulatory Activities (MedDRA) central coding dictionary, Version 22.0.
 - Data captured on the ‘Surgical Procedure History’ page of the electronic case report form (eCRF) will be presented by System Organ Class (SOC) and Preferred Term (PT).
- Medical History will be coded using the MedDRA central coding dictionary, Version 22.0.
 - Medical History conditions are defined as those conditions which stop prior to or at Screening.
 - Concomitant illnesses are identified as “Ongoing” at Screening.
 - Data captured on the ‘Medical History’ page of the eCRF will be presented by SOC and PT.
- Patients with multiple events within a SOC/PT will only be counted once for that category.

12. PRIOR AND CONCOMITANT THERAPIES AND MEDICATIONS

Prior and concomitant medications will be coded using the World Health Organization (WHO) drug code and summarized by therapeutic subgroup (Anatomical Therapeutic Chemical Classification System (ATC) level 2). Potential therapeutic subgroups include ICS, LABA, LAMA or combinations thereof, which are defined in a separate spreadsheet provided by the medic.

Prior medications will be listed for ENR set with patients classified according to randomized treatment and summarized for the RND set. Concomitant medications will be listed for ENR set with patients classified according to actual treatment received and summarized for the SAF set.

See Appendix 2 for handling of partial dates for medications. In the case where it is not possible to define a medication as prior, concomitant, or post treatment, the medication will be classified by the worst case; i.e. concomitant.

Document: ...\\Verona_Pharma\\RPL554\\BZA48916\\Biostatistics\\Documentation\\SAP\\Verona CO-205 SAP v1.0

Author: [REDACTED] Version Number: V1.0

Version Date: 05DEC2019

Template No.: CS_TP_BS016 Revision 5

Reference: CS_WI_BS005

Effective Date: 01Apr2018

- ‘Prior’ medications are medications which started prior to the first dose of study treatment and stopped prior to or on the first dose of study treatment.
- ‘Concomitant’ medications are defined as medications with onset dates on or after the first dose of study treatment and on or before last dose of study treatment, or medications with onset dates prior to first dose of study treatment without a stop date or with a stop date after first dose of study treatment.
- ‘Post treatment’ medications are defined as medications with an onset date after the date of last dose of study treatment.

Patients taking COPD medications prior to the study will be listed by therapeutic class for the ENR set, classified according to randomized treatment, and summarized by therapeutic class for the RND set.

Patient with multiple medications within an ATC level/therapeutic subgroup will only be counted once for that level.

12.1. Derivations

Time since first diagnosed with COPD = (Date of informed consent – Date of COPD first diagnosed + 1) / 365.25.

13. STUDY TREATMENT EXPOSURE

Exposure to study treatment will be presented for the SAF set.

The date of first and last study treatment administration will be taken from the e-Diary entry. The number of vials dispensed and returned will be taken from “Drug Accountability” page in the eCRF.

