5.3 Study Medication Preparation and Labelling

The vials and kits/cartons containing RPL554 and placebo will be labelled in compliance with GMP, released by a qualified person, where appropriate, and then shipped to the study center.

At Visits 2 to 5, patients will be dispensed 18 vials of study medication for twice daily dosing over 7 days (four vials provided as extras). For all visits, the first dose will be used for the in-clinic nebulization; for Visit 2 only the second dose will also be given in-clinic. The final dose administered in the morning at Visit 6 (final study visit) will be individually packaged. As such, the study medication administered in the clinic will always be stored only at the study center.

The end time of nebulization (sputtering) will be considered Time 0 for the purposes of scheduling all post-dose study procedures. Nebulization time should be approximately 5 minutes and may not exceed 10 minutes. Patients should be dosed in a well-ventilated environment, and away from other patients (i.e., in a separate location of the clinic).

For the in-clinic nebulizations, the following must be recorded in the eCRF:

- Start and end times of nebulization (times will be rounded down to the nearest minute)
- An estimation of the volume of residual product (in mL) at the end of nebulization

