5.4 Selection of Doses and Dosing Schedule

5.4.1 *Selection of Doses in the Study*

The doses of RPL554 have been selected based on the results from prior studies investigating single and multiple ascending doses in healthy subjects, single doses in asthmatics, single/multiple ascending doses in COPD patients, and up to 4 weeks of dosing in COPD patients. These twice daily doses were shown to be effective as a bronchodilator over a 12-hour dosing interval, and to provide improvement in COPD symptoms and, in general, considered safe and well tolerated.

5.4.2 *Timing of Dose for Each Patient*

Double-blind study medication is to be administered twice daily, first in the morning between 7 and 10 am, and then in the evening approximately 12 hours later. All doses for a given patient will be taken at approximately the same time each day (± 1 hour). At each visit, study medication will be administered at the study center by unblinded personnel, and the precise time of administrations shall be documented in the eCRF.

Tiotropium will be administered once-daily in the morning at approximately the same time each day, just prior to dosing with study medication.

Patients will document whether each daily dose of all study treatments was taken in the e-diary.

5.5 *Storage*

Study medication (RPL554 and placebo) should be stored below 77°F (25°C) and should not be frozen. Temperature logs should be maintained in areas where study treatment is stored. If temperature conditions have been seriously compromised or any study treatment has not been stored appropriately, this should be documented, and the study treatment quarantined until the Sponsor has been notified and confirmed whether it may be used.

Study medication will be stored under the control of the Investigator or designee in a secure facility appropriate for the advised storage conditions. Study treatments that are to be returned by the Investigator/staff or have expired must be stored separately from the unused study treatments.

Tiotropium is to be stored at room temperature 68°F to 77°F (20°C to 25°C).

5.6 *Accountability*

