- Withhold use of all long acting (once or twice daily) bronchodilators (except for tiotropium)
- Return in 7 days (± 1 day) for the next visit
- Observe the medication restrictions described in Section 5.9.1, and other restrictions described in Section 6.1
- Contact the site for any significant increase in COPD symptoms

6.6 *Treatment Period: Visit 6 (End of Study [or Early Termination])*

Patients will return for the final visit 4 weeks post-randomization. The visit shall be scheduled to begin in the morning, such that dosing occurs within 1 hour of the time of administration at Visit 2.

Patients must withhold all medications described in Section 5.9 prior to treatment in accordance with the washout times provided. If not, the visit must be rescheduled so as to occur within the permitted windows. All restrictions defined in Section 6.1 should also be adhered to.

6.6.1 *Pre-dose Assessments*

The following assessments will be performed prior to dosing:

- Concomitant medications; confirm that medications were withheld as required

- Unblinded study staff will collect nebulizer, compressor and any used/unused study medication
- Collect e-diary and review for compliance with the device
- Assessment of tiotropium and study medication compliance
- Questioning for adverse events
- Physical examination and body weight
- Blood samples for laboratory safety tests
- Urinalysis
- Urine pregnancy test (females of childbearing potential only)
- 12-lead ECG
- Vital signs
- SGRQ-C, TDI, CAT and PGAC questionnaires
- Slow spirometry (to obtain inspiratory capacity), performed 30 (\pm 10) minutes pre-dose
- Forced spirometry, performed following completion of slow maneuver
- Administration of tiotropium

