6.2. Baseline

Unless otherwise specified, baseline is defined as the last non-missing measurement taken prior to study treatment start date (including unscheduled assessments). In the case where the last non-missing measurement and the study treatment start date coincide, the measurement will be considered pre-baseline, unless time is present. If time of the assessment is on or after the study treatment start date, then the assessment is not considered baseline. AEs and medications commencing on the reference start date will be considered post-baseline.

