15.1. Derivations

E-diary compliance for study treatment will be summarized by treatment group, for the duration of the treatment, as per the following:

$100 * ((\text{total number of e-diary entries for study treatment}) / (\text{expected number of e-diary entries for study treatment during the study}))$

Each patient should have a morning and evening dose, which should be recorded in the e-diary, including the dosing at site visits, however only dosing not at the site visit will be included in the compliance calculation. At Week 4 visit there should only be morning dose recorded.

Number of e-diary entries will be calculated as per the following:

$[(\text{reference end date} - \text{reference start date}) * 2 - 1 \text{ evening dose}] - \text{expected number of CRF entries}$

The 1 evening dose will be subtracted for the completed patients.

Expected number of CRF entries for study treatment during the study will be 5 for all patients that have completed the study. In cases where patient discontinues early the following strategy explained below will be used.

1. Count how many entries there are in the "Drug Exposure" CRF dataset.
2. Select how many site visits patient should have based on the following window for each visit:
 - a. Calculate reference end day = reference end date - reference start date + 1
 - b. 0 site visits if reference end day is missing
 - c. 1 site visit if $1 \leq \text{reference end day} \leq 7$

Document: ...\\Verona_Pharma\\RPL554\\BZA48916\\Biostatistics\\Documentation\\SAP\\Verona CO-205 SAP v1.0

Author: [REDACTED] Version Number: V1.0

Version Date: 05DEC2019

Template No.: CS_TP_BS016 Revision 5

Reference: CS_WI_BS005

Effective Date: 01Apr2018

- d. 2 site visits if $8 \leq \text{reference end day} \leq 14$
- e. 3 site visits if $15 \leq \text{reference end day} \leq 21$
- f. 4 site visits if $22 \leq \text{reference end day}$

3. Choose the minimum number between points 1 and 2.

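### Dose dates come from the e-diary with no fallback, although the Visit 2 and Visit 6 doses are timed in the eCRF; collecting the diary before the Visit 6 dose can put a completer's last dose one day early

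*SAP*

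**What the plan says.** SAP 13 names one source for both dates: "The date of first and last study treatment administration will be taken from the e-Diary entry". It does not say what to do when a diary entry is missing or disagrees with the eCRF.

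The protocol gives the doses that matter in clinic. Section 5.3 uses the first dose of each supply in clinic, adding that "for Visit 2 only the second dose will also be given in-clinic". Under 6.6.2, a completer's final dose is given by unblinded staff at Visit 6. These doses have a timed record. Section 5.4.2 states that "study medication will be administered at the study center by unblinded personnel, and the precise time of administrations shall be documented in the eCRF", and 5.3 introduces its list, which includes nebulisation start and end times, with "For the in-clinic nebulizations, the following must be recorded in the eCRF".

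The diary is also meant to hold clinic doses. Protocol 5.4.2 has patients record there whether each daily dose was taken. SAP 15.1 says diary recording covers dosing at site visits, and adds: "At Week 4 visit there should only be morning dose recorded". But Protocol 6.6.1, the list of assessments to be done before dosing at Visit 6, contains the item "Collect e-diary and review for compliance with the device".

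**The concern.** The SAP takes its two anchor dates from a patient-entered record of whether a dose was taken, and passes over the site's timed record of the same doses. At Visit 6 the listed order of procedures removes the diary before the dose that SAP 13 needs to find in it.

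Two things are at stake. The last-dose date sets exposure duration (SAP 13.1) and separates concomitant from post-treatment medication (SAP 12 and Appendix 2). The first-dose date, if used as the study medication start date, decides under Appendix 2 whether an adverse event is treatment-emergent. Day 1 is not a negligible day for safety: Protocol 1.2 reports a transient increase in dizziness in multiple-dose COPD data, mostly during spirometry or dosing.

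**Working it through.** The plan states no figure to reproduce, so the check is date arithmetic on the nominal schedule.

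**Inputs**
- Visits 2 to 6 are 7 days apart (Protocol 6). With Visit 2 on Day 1, Visit 6 falls on Day 1 + 4 × 7 = Day 29.
- Duration = stop − start + 1 (SAP 13.1).
- A medication starting after the last-dose date is post-treatment (SAP 12, Appendix 2).
- An adverse event with a known onset date before the study medication start date is not treatment-emergent (Appendix 2).
- The last home dose before Visit 6 is the evening dose on Day 28, assumed taken and entered.
- Home doses on Day 2 are likewise assumed taken and entered.

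**Results for a completer**

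| Clinic doses in the diary | First dose | Last dose | Duration (days) | Event on Day 1 after dosing | Medication started Day 29 |
|---|---|---|---|---|---|
| A. All present (same as eCRF) | Day 1 | Day 29 | 29 − 1 + 1 = 29 | treatment-emergent | concomitant |
| B. Visit 6 dose absent | Day 1 | Day 28 | 28 − 1 + 1 = 28 | treatment-emergent | post-treatment |
| C. Both Visit 2 doses absent | Day 2 | Day 29 | 29 − 2 + 1 = 28 | not treatment-emergent* | concomitant |
| D. Visit 2 and Visit 6 doses absent | Day 2 | Day 28 | 28 − 2 + 1 = 27 | not treatment-emergent* | post-treatment |

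*Only if the SAP 13 date is used as the study medication start date in Appendix 2.

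Case B is what Protocol 6.6.1 produces if its order is followed and nobody enters the Week 4 dose. The loss is 1 day in 29, or 3.4%. Treatment-emergent status does not change in case B, because the definition in SAP 17.1 has no upper date limit. The Visit 6 order therefore bears on duration and medication class, not on adverse events.

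Cases C and D need a different failure: both Day 1 doses missing from a diary the patient has held since Visit 1. One Day 1 entry is enough to keep the start date right, since only the date matters.

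**Diary compliance.** SAP 15.1 computes expected entries for a completer as (reference end − reference start) × 2 − 1 − 5. If its reference dates come from SAP 13, which is an assumption, the denominator is 28 × 2 − 6 = 50 in A, 27 × 2 − 6 = 48 in B and C, and 26 × 2 − 6 = 46 in D.

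**Who is reached.** Protocol 4.4.5 expects about 360 of 400 patients to complete, so case B could apply to at most about that number. Patients with an early termination visit are not dosed at it (Protocol 6.6.2), so the Visit 6 order does not affect them.

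**The case against.** The strongest reply is that the plan intends the diary to hold every dose. Protocol 5.4.2 makes no exception for clinic doses, and SAP 15.1 expressly includes them. The SAP's weekly diary and rescue means (16.2.1.2.1 and 16.2.1.4) count the final visit day for completers, so its authors assumed the diary was still in use then. All of this stands. It means a reader should not infer that every completer's last-dose date will be wrong: the error needs the 6.6.1 order to be followed and no Week 4 entry to be made. What it does not do is remove the conflict between 6.6.1 and 15.1.

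A reader might also infer that Day 1 adverse events will routinely lose treatment-emergent status. The documents do not support that. A Day 1 entry is planned, and SAP 6.1 defines the reference start as the day of first dose without tying it to the SAP 13 source. It remains a missing-entry risk. Such gaps are foreseeable, since Protocol 4.3 admits patients who completed the diary on 5 of the last 7 run-in days and 7.2.7 records a deviation only below 75% compliance. The documents give no rate for missing Day 1 entries, so no patient count can be put on it.

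A third tempting reading is that a Day 2 start would make a Day 1 post-dose vital sign or ECG the safety baseline, because under SAP 6.2 "baseline is defined as the last non-missing measurement taken prior to study treatment start date (including unscheduled assessments". But that is a default that yields to other specifications. Protocol 9.4.7 fixes the safety baseline at pre-dose on Visit 2, and SAP 3.3 plans no change from the protocol. SAP 16.1.2 separately ties the FEV₁ baseline to the pre-dose reading on Day 1.

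Finally, the effects are small. Total exposure in mg rests on vial counts (SAP 13.1), safety data are not compared statistically unless specified (SAP 17), and events or medications that cannot be classified default to treatment-emergent or concomitant (SAP 17.1 and 12). That default does not help here, because a wrong but complete date leads to a definite classification.

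**Conclusion.** The point holds and is minor. SAP 13 names the e-diary as the only source for two dates that, for completers, belong to clinic doses timed in the eCRF. Protocol 6.6.1 and SAP 15.1 disagree on whether the diary can contain the last of those doses.

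If 6.6.1 is followed and no Week 4 entry is made, a nominal completer's last-dose date is Day 28 rather than Day 29, duration is 28 rather than 29 days, and a medication started on the Visit 6 day is classed as post-treatment. This assumes the Day 28 evening dose was taken and entered.

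The adverse event consequence is separate and doubly conditional: both Day 1 doses must be missing from the diary, and the SAP 13 date must be used in Appendix 2. The FEV₁ baseline, the primary endpoint and the protocol's safety baseline are not affected. The reach is limited to descriptive exposure and to the classification of medications and adverse events.

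**What to change.** In SAP 13, take the first dose date and time from the Visit 2 nebulisation record in the eCRF. Define the last dose date as the later of the last in-clinic dose in the eCRF and the last e-diary entry confirming that a dose was taken. The diary then decides the date only for patients whose last dose was at home. State which record prevails if the two disagree or an entry is missing.

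Name these as the reference start and end dates in SAP 6.1, which at present defines only the start and gives no source, and use them in SAP 12, 15.1 and Appendix 2. Reconcile SAP 15.1 with Protocol 6.6.1, so that either the diary is available for the Visit 6 dose or the SAP no longer expects that entry.

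The cost is a short SAP edit with matching cross-references and programming. No new data are needed: the protocol already requires the clinic dosing times, and SAP 15.1 already draws on the Drug Exposure CRF dataset.

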13.1. Derivations

The RPL554 exposure will be calculated as:

Duration of exposure (in days) to study treatment:
(stop date – start date) +1

Total exposure (in mg):
(Number of vials dispensed - Number of vials returned) x Content of each vial in mg

The mean duration of exposure in days and the mean exposure in mL will be summarized by treatment group.

Document: ...\\Verona_Pharma\\RPL554\\BZA48916\\Biostatistics\\Documentation\\SAP\\Verona CO-205 SAP v1.0

Author: [REDACTED] Version Number: V1.0

Version Date: 05DEC2019

Template No.: CS_TP_BS016 Revision 5

Reference: CS_WI_BS005

Effective Date: 01Apr2018

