Between clinic visits, patients will self-administer both tiotropium and study medication every morning at home in the same order as described above, while only study medication treatment will be taken in the evening.

Patients will be instructed to withhold study treatments (including tiotropium) and rescue albuterol prior to all study visits, and to bring their e-diary, open-label tiotropium and nebulized study medication to all study visits. Patients will be instructed to withhold albuterol for at least 6 hours prior to all visits.

Patients will return for three interim, weekly visits (Visits 3, 4 and 5), where they will return used and unused double-blind study medication and receive new study medication from the unblinded study staff. The first dose of the newly dispensed study medication will be administered in the clinic with spirometry performed for 3 hours after dosing. Questionnaires, safety assessments, study treatment compliance (including tiotropium) and e-diary review will be conducted at Visits 2 through 5. Blood samples for PK analysis will be collected pre-dose at Visits 2 and 4.

At the End of Study visit (Visit 6) (after 4 weeks of treatment, or early termination), patients will take their last dose of tiotropium and study medication, and will be resident at the study center from the morning until at least 12 hours after dosing to allow for monitoring of lung function and study closeout procedures. A phone call will occur approximately 1 week after the final visit as a safety follow-up.

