9.4 Statistical Methods

In general, unless stated otherwise, continuous variables will be summarized using descriptive statistics (number of patients, mean, standard deviation, median, minimum and maximum values) and for categorical (nominal) variables, the number and percentage of patients will be used.

All hypothesis testing will be done using two-sided alternative hypotheses. P-values less than 5% will be considered statistically significant.

9.4.1 *Patient Disposition*

The number of patients enrolled, randomized, completed or withdrawn (with reason for withdrawal) will be summarized.

9.4.2 *Protocol Deviations*

All protocol deviations collected will be divided into critical, major or minor categories. Prior to database lock protocol deviations will be reviewed and consequences for inclusion of patients in various analysis population sets determined and documented.

9.4.3 *Demographics and Other Baseline Characteristics*

Demographics and baseline characteristics (including pre- and post-bronchodilator FEV₁ [both in liters and in percentage of predicted normal], post-bronchodilator FEV₁/FVC, FEV₁ reversibility, duration of COPD [time since diagnosis], smoking habits including number of pack years, number of patients taking prior COPD medications by therapeutic class including ICS, LABA, LAMA or combinations thereof) will be listed and summarized appropriately.

Medical history, prior and concomitant medications, viral serology results, mMRC score, pregnancy test and/or FSH test results from females and chest X-ray findings will be listed.

9.4.4 *Extent of Exposure and Treatment Compliance*

Compliance will be calculated based on two parameters – the number of used and unused vials returned and the dosing recorded in the e-diary. Total exposure will be based on the compliance with dose and the dose group the subject was randomized into. For in-clinic dosing, the RPL554 exposure will be calculated based on the nominal dose.

9.4.5 *Efficacy/Pharmacodynamics*

The FAS will be the primary efficacy population; outcomes based on the PPS will be considered as a sensitivity analysis.

FEV₁ and FVC will be summarized as actual value and change from baseline using descriptive statistics over time for all treatments and both study parts.

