14.1. Derivations

Treatment compliance will be summarized by treatment group in 2 ways:

- $100 * ((\text{total number of vials dispensed} - \text{total number of vials returned}) / (\text{expected number of vials to be taken during the study}))$
- Drug intake as recorded in the e-diary: percent of 'yes' responses. The denominator is the number of records for which the patient provided an answer (Yes or No) to drug intake questions (morning and evening) in the e-diary.

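### Unless the eCRF counts only unused vials as returned, dispensed minus returned in SAP 13.1 and 14.1 does not measure doses taken

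*SAP*

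**What the plan says.** SAP 13.1 defines total exposure in mg as "Number of vials dispensed - Number of vials returned", multiplied by the mg content per vial. SAP 14.1 takes the same difference in vial totals, divides it by the "expected number of vials to be taken during the study" and expresses the result as a percentage. SAP 13 gives the source of the counts: "The number of vials dispensed and returned will be taken from" the Drug Accountability page of the eCRF. Neither section says whether a returned vial is a used one, an unused one, or either.

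The protocol is explicit that both kinds come back. Section 3.1 says of Visits 3 to 5 that "they will return used and unused double-blind study medication". Sections 6.5.1 and 6.6.1 have unblinded staff collect used and unused medication at Visits 3 to 5 and at Visit 6. Section 5.6 includes used vials in the medication sent back after accountability. Section 9.4.4 rests compliance on "the number of used and unused vials returned and the dosing recorded in the e-diary". SAP 3.3 states that no changes to the protocol's analyses are planned.

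**The concern.** A dispensed-minus-returned count gives doses taken only if the vials that come back are unused. The protocol's compliance rule depends on telling used from unused vials, and the SAP formulas drop that distinction. If used vials are included in the returned count, they are subtracted along with the leftovers, and what remains is the number of vials that never came back. A patient who takes every dose and returns every vial would then look as if no drug had been taken, and a patient who returns nothing would look over-compliant.

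At stake are total exposure in mg and one of the two compliance measures, both reported by treatment group on the safety set in a dose-ranging study. The SAP gives no second derivation of exposure in mg. The other compliance measure, e-diary intake, uses only answered records as its denominator, so unanswered doses drop out. The vial count is the measure that does not depend on diary answers.

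**Working it through.** **Inputs**
- 18 vials at each of Visits 2 to 5, of which 4 are extras (Protocol 5.3).
- One individually packaged vial for the Visit 6 morning dose (Protocol 5.3 and 6.6.2).
- In-clinic doses: two at Visit 2 and one at each of Visits 3, 4, 5 and 6 (Protocol 5.3), so 2 + 4 = 6.
- Nominal 7-day intervals between visits, with twice-daily dosing.

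**The protocol's own figure.** 7 days × 2 doses + 4 extras = 18 vials per visit, which reproduces the stated number. The documents state no exposure or compliance value to compare with.

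**Nominal completer**
- Dispensed: 4 × 18 + 1 = 73
- Doses due: 4 × 14 + 1 = 57
- Unused if fully adherent: 73 − 57 = 16

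**SAP formulas under three meanings of returned, for a fully adherent patient**

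| Vials counted as returned | Returned | Dispensed − returned | Compliance | Exposure, 3.0 mg arm |
|---|---|---|---|---|
| All used and unused | 73 | 0 | 0/57 = 0% | 0 mg |
| All except the six used in clinic | 73 − 6 = 67 | 6 | 6/57 = 10.5% | 6 × 3.0 = 18 mg |
| Unused only | 16 | 57 | 57/57 = 100% | 57 × 3.0 = 171 mg |

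With unused vials only, the other arms give 57 × 0.375 = 21.375 mg, 57 × 0.75 = 42.75 mg and 57 × 1.5 = 85.5 mg.

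**Does the first meaning track adherence?** No. A patient who takes half the doses and returns all 73 vials also scores 73 − 73 = 0, or 0%. A patient who returns nothing scores 73/57 = 128%.

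**Sensitivity to the assumptions**
- Visit 6 vial not counted as dispensed: 4 × 18 = 72 dispensed, 4 × 14 = 56 due, 16 unused. The first meaning still gives 0%. The second leaves five clinic vials, 5/56 = 8.9%.
- Visit windows of ±1 day on each of four intervals: 24 to 32 days, so 2 × 24 + 1 = 49 to 2 × 32 + 1 = 65 doses due. The first meaning still gives 0%. The second gives 6/65 = 9.2% to 6/49 = 12.2%.

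**The case against.** The strongest reply is that the formulas depend on an eCRF page that the documents do not show. Because Protocol 9.4.4 names used and unused vials, the page may well record them separately. If the SAP's returned count is the unused field, both formulas give the right answer and only the wording is at fault. The context also shows the intent: dividing by vials expected to be taken, or multiplying by vial content to obtain mg, makes sense only if the difference means vials taken. A programmer would probably notice a table of zeros.

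This stands as a limit on the conclusion. A reader might infer that the reported exposure and compliance tables will be wrong; the documents do not support that without the eCRF definition. They do support saying that the SAP text, read with the protocol's use of the word, gives the wrong figure. Relying on someone to notice it would leave the repair until after database lock, and partial returns could produce values that are wrong but not obviously so.

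A second reply is that 0% is an extreme. Protocol 5.3 keeps clinic-administered medication at the site, and Table 4 lists dispensing only at Visits 2 to 5, so the six clinic vials may never be logged as returned. That stands too, and is why the result is a range.

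The sentence in Protocol 5.6 about unused vials going back to the sponsor at study end does not settle the matter. It concerns shipment to the sponsor and does not define the SAP term, and the paragraph before it counts used vials among returned medication.

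**Conclusion.** The derivation is wrong as written when read with the protocol's meaning of returned. For a fully adherent completer it gives 0% to about 10.5% vial compliance instead of 100%, and 0 to 18 mg instead of 171 mg in the 3.0 mg arm. This assumes nominal visit spacing, the Visit 6 vial counted as dispensed, every vial accounted for, and an eCRF returned field that is not confined to unused vials. If that field holds unused vials only, the numbers would be right and the defect is one of definition.

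The reach is small. E-diary compliance and duration of exposure in days do not use the formula, and neither does the primary efficacy model. It would also go too far to treat the vial count as the main compliance measure: Protocol 9.4.4 and SAP 14.1 list two measures without ranking them.

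**What to change.** In SAP 13.1 and 14.1, replace vials returned with unused vials returned, and name the Drug Accountability field that holds that count. Add a sentence on how clinic-administered vials are counted, including the separately packaged Visit 6 vial, so that numerator and denominator cover the same doses. Add another on how lost vials are treated.

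The cost is a short wording change in two formulas and a check of one eCRF page. The downside is small: an unused vial that is lost would count as taken. Building the count from used vials returned plus documented clinic doses is less attractive, because clinic doses would be counted twice if the site also logs those vials as used, and home doses whose empty vials are lost would be missed.

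SAP 13.1 can be corrected on units in the same edit: it derives exposure in mg but says that mean exposure will be summarized in mL.
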